2 ANALYSIS POPULATIONS

The following populations for analyses are defined. Unless otherwise specified, these populations will be applicable for both safety run-in and core phase parts. The participants included in the safety run-in part, if fulfilling the inclusion criteria of the core phase part and if the planned dose and dosing schedule are the same as in core phase will be included in the analyses of core phase.

Table 4 - Populations for analyses

Population	Description
Screened	All participants who have been given the informed consent form.
Enrolled	All participants who have given their informed consent and have been allocated to an intervention (by IRT) regardless of whether the intervention was received or not.
Exposed	All participants who have given their informed consent and received at least one dose (even incomplete) of IMP (SAR444245 or pembrolizumab).
Population without trial impact (disruption) due to COVID-19	All exposed participants: 
without any critical or major deviation related to COVID-19and who did not permanently discontinue treatment due to COVID-19and who did not permanently discontinue study due to COVID-19.
Efficacy	All participants from the exposed population with at least one evaluable post-baseline tumor assessment or who permanently discontinued study treatment.
DLT-evaluable ^a	All exposed participants in safety run-in part who have been treated and observed for DLT observation period (defined in the individual substudy). Any participants who have experienced a DLT during DLT observation period will also be DLT-evaluable.
Response evaluable	All participants from the efficacy population with at least one baseline and one evaluable post-baseline tumor assessments. Participants who died from disease progression before any TA will also be response-evaluable.
Pharmacokinetic (PK)	All participants from the exposed population with at least 1 PK concentration available after the first dose of study intervention.
ADA	All participants from exposed population with at least 1 ADA result (positive, negative or inconclusive) after the first dose of study intervention.
Pharmacodynamics (PDy)	All participants from the exposed population with at least 1 PDy (biomarker) parameter assessed after the first dose of study intervention.

^a The dose-limiting toxicity (DLT) observation period is 21 days for Cohort A, and 28 days for Cohort C1.

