3.7.1.2 Immunogenicity analyses

Participant's ADA status, response variable and kinetics of ADA responses (see definitions below) will be summarized on the ADA population.

Kinetics of ADA responses will be described for participants with treatment-induced ADA and for participants with treatment-boosted ADA, separately. Time to ADA onset and duration of ADA will be described with minimum, Q1, median, Q3 and maximum statistics.

Peak titer will be described with minimum, Q1, median, Q3 and maximum statistics for participants with treatment-induced ADA and for participants with treatment-boosted ADA, separately.

ADAs against SAR444245 (negative, positive, inconclusive) and corresponding titers, ADAs directed against PEG moiety of SAR444245 status (negative, positive,) and ADAs cross-reacting with endogenous IL-2 status (negative, positive) will also be described overtime using descriptive statistics.

ADAs directed against PEG moiety of SAR444245 status and ADAs cross-reacting with endogenous IL-2 status will only be determined if ADAs against SAR444245 status is positive.

The impact of positive immune response on efficacy, PK and safety variables may be further explored, depending on ADA incidence.

Participant's ADA status against SAR444245

- Participants with **pre-existing ADAs** correspond to participants with ADAs present in samples drawn before first administration of intervention. Participants with missing ADA sample at baseline will be considered as without pre-existing ADA.
- Participants with **treatment-emergent ADA** correspond to participants with at least one treatment-induced/boosted ADA.
 - Participants with **treatment-induced ADAs** correspond to participants with ADAs that developed during the treatment-emergent (TE) period and without pre-existing ADA (including participants without pre-treatment samples).
 - Participants with **treatment-boosted ADAs** correspond to participants with pre-existing ADAs that are boosted during the TE period to a significant higher titer than the baseline. A 2-fold serial dilution schema is used during titration, so at least a 4-fold increase will be considered as significant.
- Participants with **unclassified ADA** correspond to participants with pre-existing ADAs that cannot be classified as treatment-boosted ADA because of missing titer(s) (i.e., a positive ADA sample during the TE period in a participant with pre-existing ADA but with missing titer at this sample or at baseline).

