- Participants **without treatment-emergent ADA** correspond to participants without treatment-induced/boosted ADA and without any inconclusive sample nor unclassified ADA during the TE period.
- Participants **with inconclusive ADA** are defined as participants which cannot irrefutably be classified as with or without treatment-emergent ADA.

Kinetics of ADA response

[figure not shown]
Kinetics of ADA response will be derived for participants with treatment-induced/boosted ADA considering ADA samples collected during the TE period and post-treatment period.

- **Time to onset of ADA response** is defined as the time period between the first IMP administration and the first treatment-induced/boosted ADA.
- **Duration of ADA response** is defined as the time between the first treatment-induced/boosted ADA and the last treatment-induced/boosted ADA, irrespective of negative samples or positive samples not reaching the boosted threshold in-between. ADA duration will be summarized only for participants with persistent ADA response.
 - A positive sample (boosted positive sample for participants with pre-existing ADA) occurring after the TE period will be considered as treatment-induced/boosted ADA if a previous treatment-induced/boosted ADA occurred during the TE period and less than 16 weeks before this sample.
- **Persistent ADA response** is defined by treatment-induced/boosted ADA with a duration of ADA response of at least 16 weeks.
- **Transient ADA response** is defined by treatment-induced/boosted ADA with a duration of ADA response of less than 16 weeks and the last sample of the TE period is not treatment-induced/boosted.
- **Indeterminate ADA response** is defined by treatment-induced/boosted ADA that are neither persistent nor transient.

ADA response variable:

- **ADA incidence** is defined as the proportion of participants found to have seroconverted (treatment-induced ADAs) or boosted their pre-existing ADA response (treatment-boosted ADAs) at any time point during the TE period.
- **Incidence of ADAs** directed against PEG moiety of SAR444245 is defined as the proportion of participants with ADAs directed against PEG moiety of SAR444245 during the TE period among evaluable participants. Participants from ADA population are evaluable for ADAs directed against PEG moiety except if ADAs directed against PEG moiety status is not determined on an ADA against SAR444245 positive sample

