- **Incidence of ADAs cross-reacting with endogenous IL-2** is defined as the proportion of participants with ADAs directed against endogenous IL-2 during the TE period among evaluable participants. Participants from ADA population are evaluable for ADAs directed against endogenous IL-2 except if their status is not determined on an ADA against SAR444245 positive sample.

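### As literally worded, the SAP's evaluability rule for anti-PEG and IL-2-cross-reacting ADA can drop a participant already shown to be positive, if another ADA-positive sample lacks a specificity result

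*SAP*

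**What the plan says.** SAP 3.7.1.2, in the definitions of the ADA response variables, gives the anti-PEG incidence as the "proportion of participants with ADAs directed against PEG moiety of SAR444245 during the TE period among evaluable participants". The next sentence sets evaluability: "Participants from ADA population are evaluable for ADAs directed against PEG moiety except if ADAs directed against PEG moiety status is not determined". It ends by tying the exclusion to a single sample: "status is not determined on an ADA against SAR444245 positive sample". For IL-2 cross-reactivity, members of the ADA population are likewise "evaluable for ADAs directed against endogenous IL-2 except if their status is not determined on an ADA against SAR444245 positive sample".

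Three other provisions bear on how the rule works:

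- Both specificities "will only be determined if ADAs against SAR444245 status is positive" (SAP 3.7.1.2).
- The ADA population is "All participants from exposed population with at least 1 ADA result (positive, negative or inconclusive) after the first dose of study intervention" (SAP section 2).
- For overall ADA, SAP 3.7.1.2 works differently. Participants with treatment-emergent ADA "correspond to participants with at least one treatment-induced/boosted ADA". An incomplete sample matters only for the negative class, which must be "without any inconclusive sample nor unclassified ADA during the TE period".

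**The concern.** A participant with a determined PEG-positive or IL-2-cross-reactive sample in the TE period is an event, whatever the other samples show. The evaluability sentences make no exception for such a participant. A programmer who follows them would delete a documented positive because some other ADA-positive sample was not characterised.

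Two features add to this:

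- **Different time windows.** The numerator is limited to the TE period; the exclusion is not. An uncharacterised pre-dose sample can remove a participant. So can an end-of-treatment sample: that visit is 30 (±7) days after the last dose (section 1.5 of both substudies), while the TE period ends 30 days after it (SAP 3.1).
- **One-sided exposure.** Only ADA-positive samples are characterised, so an ADA-negative participant can never become non-evaluable. Each further ADA-positive sample gives a participant another chance of removal.

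At stake are two participant-level proportions, one of them on antibodies to an endogenous cytokine, in cohorts of about 25, where one lost positive is visible.

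**Working it through.** The plan states no figure for either incidence, so there is nothing to reproduce.

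**1. Inputs**

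- From the documents: 25 participants per cohort (SAP section 4). ADA samples are taken at C1D1, C1D8, Cycles 2, 4, 7 and 10, every 5th cycle and end of treatment (section 1.5 of both substudies). If every 5th cycle means 15, 20, 25 and so on, the maximum is 9 + 3 = 12 samples over 35 cycles (Cohort A) and 12 + 3 = 15 over 52 cycles (Cohort C1). The sponsor may stop ADA sampling earlier.
- Not in the documents, so assumed below: the ADA rate, the share of ADA-positive participants with a given specificity, the number of ADA-positive samples each, and the proportion of those without a specificity result.

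**2. SAP rule against an any-positive rule**

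Let n be the participants evaluable when any TE positive counts, x of them positive, and k of those x with another, undetermined ADA-positive sample.

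- Any-positive incidence: x/n
- SAP incidence: (x − k)/(n − k)
- Difference: x/n − (x − k)/(n − k) = k(n − x)/[n(n − k)], which is never negative and is zero when k = 0

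| n | x | k | SAP rule | Any-positive rule |
|---|---|---|---|---|
| 25 | 4 | 0 | 4/25 = 16.0% | 4/25 = 16.0% |
| 25 | 4 | 1 | 3/24 = 12.5% | 4/25 = 16.0% |
| 25 | 4 | 2 | 2/23 = 8.7% | 4/25 = 16.0% |
| 25 | 2 | 2 | 0/23 = 0% | 2/25 = 8.0% |

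**3. SAP rule against the truth**

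Let a be the ADA rate, π the share of ADA-positive participants with the specificity, m the ADA-positive samples each, and q the chance that a sample is undetermined. Assume q is unrelated to specificity and status is constant within a participant. With c = (1 − q)^m, the chance that all results are complete:

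- True incidence: aπ
- SAP incidence: aπc/(1 − a + ac)
- Any-positive incidence: aπd/(1 − a + aπd + a(1 − π)c), with d = 1 − q^m

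| a | π | m | q | True | SAP rule | Any-positive rule |
|---|---|---|---|---|---|---|
| 0.3 | 0.5 | any | 0 | 15.0% | 15.0% | 15.0% |
| 0.3 | 0.5 | 1 | 10% | 15.0% | 13.9% | 13.9% |
| 0.3 | 0.5 | 3 | 10% | 15.0% | 11.9% | 15.6% |
| 0.3 | 0.5 | 5 | 20% | 15.0% | 6.2% | 16.7% |
| 0.5 | 0.5 | 5 | 20% | 25.0% | 12.3% | 30.0% |

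Third row in full: c = 0.9³ = 0.729. SAP: 0.15 × 0.729/(0.7 + 0.3 × 0.729) = 0.10935/0.9187 = 11.9%. Any-positive: d = 0.999, so 0.14985/(0.7 + 0.14985 + 0.10935) = 15.6%.

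**4. Where the downward direction fails**

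- If everyone is ADA-positive (a = 1), the SAP formula reduces to π, the truth, and there is no bias.
- If missing results concentrate in specificity-negative participants, the sign can reverse. Take 4 true positives of 25. With one positive and six negatives removed, the SAP rule gives 3/18 = 16.7%; with no positive and two negatives removed, 4/23 = 17.4%. The truth is 16.0%.

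**The case against.** The strongest reply is that the rule may never bite. Specificity testing follows ADA positivity, and nothing in the documents says results will be missing. That is right as far as it goes: with complete results there is no effect. But the SAP writes a rule for undetermined status, and protocol 8.7 makes further characterisation of immunogenicity optional, so gaps are foreseeable.

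A second reply is that positives are not hidden. SAP 3.7.1.2 also describes PEG and IL-2 status over time, with no evaluability restriction. The named secondary endpoint, incidence of ADA against SAR444245, does not use this rule. All of it is descriptive, and neither document ties a decision to these two proportions. This stands, and it limits the severity.

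A third reply is that the IL-2 sentence can be read at participant level, and that the TE period in the incidence definition was meant to govern evaluability too. Both are possible intentions, but neither is written, and the anti-PEG sentence is plainly about a sample. If that is the intent, the same edit makes it explicit.

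A reader might go further and infer that the plan does discard positives and that both incidences are biased downward. The documents do not support this. They give no missing rate, and the direction relative to the truth depends on who has the missing results. Calculations in which only specificity-positive participants can be removed give an extreme. With 10 positives of 25, m = 5 and q = 10%, the SAP figure is 5.9/20.9 = 28% if only those 10 are ADA-positive. It is 5.9/14.8 = 40%, the true value, if all 25 are.

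**Conclusion.** The evaluability wording is wrong as written; severity is low. Taken literally, it lets an uncharacterised ADA-positive sample, inside or outside the TE period, override a documented TE positive. That is the reverse of how SAP 3.7.1.2 treats overall ADA.

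The only guaranteed result is that each reported incidence is at or below the any-positive incidence, and strictly below it once a documented positive is removed while some evaluable participants are not positive. Bias relative to the truth is downward if missingness is unrelated to specificity and some participants are ADA-negative. Otherwise it can vanish or reverse. Its size cannot be derived from the documents, and every percentage above rests on assumed counts or rates. The primary efficacy analyses, the overall ADA incidence and the summary of specificity status over time are unaffected.

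**What to change.** In SAP 3.7.1.2, replace the evaluability sentence in both definitions with wording to this effect:

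- A participant with at least one TE sample positive for the specificity is evaluable and counted as positive.
- A participant is non-evaluable only if no TE sample is positive for that specificity and at least one ADA-positive TE sample has undetermined status.
- The number of non-evaluable participants is shown next to each incidence.

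The count is needed because the new rule drops only unresolved participants without a documented positive, which can push the figure upward: 15.6% against a true 15.0% in the moderate case above, and more under heavy missingness (30.0% against 25.0%). It also cannot recover a participant whose only ADA-positive sample is undetermined (the m = 1 row).

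The cost is a short rewording of each definition, a small programming change and one extra count per table. No new samples or assays are needed. Settling it before the data are reviewed avoids a later choice about known positives.

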3.7.1.3 Biomarker analyses

3.7.2 Subgroup analyses

Subgroup analyses of the primary efficacy endpoint will be performed to assess the homogeneity of the treatment effect across the following subgroups (categories with fewer than 5 participants may be combined with other categories):

- Sex (M, F)
- Age categories (12 to <18, 18 to <65, 65 to <75, ≥ 75)
- ECOG performance status at baseline
- Previous autologous HSCT (Y/N)
- Previous brentuximab vedotin use (Y/N)
- No. number of lines of previous therapy (e.g., 0, 1-2 vs ≥ 3 ?)

The ORR will be provided, as well as the corresponding 90% CI, for each subgroup, using the same method as applied to the primary analysis.

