1.1 STUDY DESIGN

This is a Phase 2, multi-cohort, un-controlled, non-randomized, open-label, multi-center study assessing the antitumor activity and safety of SAR444245 with or without other anticancer therapies in adults and adolescents with relapsed or refractory B cell lymphoma.

After a screening period of up to 28 days, participants who fulfill eligibility criteria of any cohort will be enrolled to the safety run-in of that cohort depending on the type of lymphoma and the number of prior lines therapy:

- **Cohort A (3L/4L cHL)** will include 25 participants with classic Hodgkin lymphoma (cHL) who have received at least 2 or 3 lines of systemic therapy and will assess SAR444245 **combined with pembrolizumab** as at least 3rd or 4th line of therapy.
- Cohort C1 (3L DLBCL post-CAR-T) will include 25 participants with diffuse large B cell lymphoma (DLBCL) who have received at least 2 lines of systemic therapy and are post-CAR-T and will assess SAR444245 monotherapy regimen as at least 3rd line of therapy.

A safety run-in will confirm the dose of SAR444245 in each cohort. The dose confirmation will proceed using Modified Toxicity Probability Interval Design (mTPI-2 design, Guo et al 2017 (1)) Participants who fulfill the eligibility criteria of any cohort may be enrolled to the safety run-in of that cohort. After a maximum of 10 participants have been enrolled into a specific cohort, enrollment will be paused for that cohort.

Once at least 6 participants are evaluable for dose limited toxicity (DLT) in a specific cohort, safety data for these participants will be reviewed by the Study Board. DLT-evaluable participants include all participants in the safety run-in part who have been observed for the DLT observation period (defined in the individual cohort). Any participant who experienced a DLT at any time during the DLT observation period will also be DLT-evaluable. If after recruiting the first 10 participants there are fewer than 6 participants evaluable for DLT, more participants will be enrolled to ensure at least 6 DLT evaluable participants. Participants who are enrolled in the safety run-in and treated at the confirmed safe dose will be included in the total number of participants for that specific cohort.

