3.2.2 Main analytical approach

The primary endpoints, CRR and ORR, will be analyzed with estimand 1 introduced in [Section 1.2.1](#). These endpoints are defined according to the following attributes:

- The endpoint complete response (CR) for cohort A
- The endpoint objective response (CR or PR) for cohort C1
- The treatment condition is SAR444245
 - in combination with pembrolizumab for Cohort A
 - in monotherapy for Cohort C1
- The analysis population is the efficacy population
- Intercurrent events (IE):
 - The new anticancer therapy IE will be handled with the “while not initiating new anti-cancer therapy” strategy; the primary endpoints will be assessed based on tumor assessments up to the time of new anticancer therapy.
 - The early IMP discontinuation IE will be handled with the “treatment policy” strategy; the primary endpoints will be assessed based on tumor assessments irrespective of the IMP discontinuation.

Population-level summary: Will include the - CRR (cohort A) and ORR (cohort C) and corresponding confidence interval using the Clopper Pearson exact method.

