3.3.1 Efficacy secondary endpoint(s)

3.3.1.1 *Definition of endpoint(s)*

The secondary efficacy endpoints are:

- The ORR is defined as the proportion of participants who have a CR or PR as BOR, for cohort A.
- The CRR is defined as the proportion of participants who have a CR as BOR, for cohort C1.
- The TTR is defined as the time from the first administration of IMP to the first tumor assessment at which the overall response was recorded as PR or CR determined by Investigator.

- The duration of response (DoR) is defined as the time from the first tumor assessment at which the overall response was recorded as PR or CR until progressive disease (PD) determined by Investigator, or death from any cause, whichever occurs first.
- The clinical benefit rate (CBR) is defined as the proportion of participants with clinical benefit (CR or PR as BOR, or SD lasting at least 6 months (i.e., 26 weeks or later from first IMP intake, allowing for the ± 7 days visit window for tumor assessment scheduled at 27 weeks) determined by Investigator per Lugano response criteria 2014.
- Progression free survival (PFS) defined as the time from the date of first IMP administration to the date of the first documented disease progression determined by Investigator or death due to any cause, whichever occurs first.

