4 SAMPLE SIZE DETERMINATION

As this study is not intended to explicitly test a hypothesis, calculations of power and Type I error were not considered in the study design. No formal testing procedure is going to be considered.

The study will start with a safety run-in with 6-10 participants from each cohort. Participants who are enrolled in the safety run-in and treated at the confirmed safe dose will be included in the total number of participants from their given cohort. The plan is to treat a total of approximatively 75 participants: 25 participants in Cohort A and C1.

Table 10 - Estimated complete response rate (CRR) and objective response rate (ORR) with 90% confidence interval according to number of responders

Cohort A and C1	
Number of Responders (N=25)	CRR or ORR in % (90%CI*)
1	4 % (0.2% - 17.6%)
3	12 % (3.4% - 28.2%)
4	16 % (5.7% - 33%)
5	20 % (8.2% - 37.5%)
6	24 % (11% - 42%)
8	32 % (17% - 50.4%)
9	36 % (20.2% - 54.4%)

* Clopper-Pearson confidence interval

Cohort A and C1: With a sample size of 25 participants, the probability of observing 1 or more instances of a specific AE with a true incidence rate of 1%, 2% or 5% is 22.2%, 39.7% or 72.3% respectively.

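### SAP 3.7.2 names only ORR for the subgroup analyses of the primary endpoint, although Cohort A's primary endpoint is CRR; SAP Section 4 states about 75 participants where two cohorts of 25 give 50

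*SAP*

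**What the plan says.** **Subgroups.** SAP 3.7.2 opens with "Subgroup analyses of the primary efficacy endpoint will be performed". It lists six factors: sex, age group, ECOG status, previous autologous transplant, previous brentuximab vedotin and number of previous lines. It then gives one output sentence, "The ORR will be provided, as well as the corresponding 90% CI, for each subgroup", which closes with "using the same method as applied to the primary analysis".

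The primary analysis in SAP 3.2.2 is split by cohort. It specifies "The endpoint complete response (CR) for cohort A" and objective response for Cohort C1, and its summary measure is "CRR (cohort A) and ORR (cohort C) and corresponding confidence interval using the Clopper Pearson exact method". SAP Table 2, 3.1 and 3.2.1 agree, as does 9.4.2 of Substudy 01 and of Substudy 03. SAP 3.3.1.1 puts ORR among the secondary endpoints for Cohort A: "The ORR is defined as the proportion of participants who have a CR or PR as BOR, for cohort A".

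**Total.** SAP Section 4 states: "The plan is to treat a total of approximatively 75 participants: 25 participants in Cohort A and C1". SAP 1.1 describes exactly two cohorts, each of 25, and SAP Table 3 also counts two. Section 9.2 of each substudy protocol plans 25 participants at the confirmed safe dose.

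**The concern.** For Cohort A, 3.7.2 gives two instructions that cannot both be followed. The opening sentence calls for CRR; the output sentence calls for ORR. The text does not plainly drop CRR, so the programmer must guess or ask. If the output sentence is taken literally, Cohort A's secondary endpoint appears under a primary-endpoint heading.

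The choice should be fixed in advance. The study is open-label, response is assessed by the Investigator, and SAP 3.8 allows informal interim looks. A choice between two response endpoints left open until Cohort A's responses are visible is harder to defend, even in a descriptive study.

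The total is a simpler matter: the SAP's sample size section states a sample size that the design does not have.

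**Working it through.** **1. Subgroup endpoint.** No arithmetic decides this, so the statements are set side by side.

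| Source | Cohort A | Cohort C1 |
|---|---|---|
| Primary endpoint (SAP 3.2.1, 3.2.2) | CRR | ORR |
| Secondary response endpoint (SAP 3.3.1.1) | ORR | CRR |
| 3.7.2, opening sentence implies | CRR | ORR |
| 3.7.2, output sentence names | ORR | ORR |
| Do the two sentences of 3.7.2 agree? | No | Yes |

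The closing clause on method does not settle it. The primary method is an exact Clopper-Pearson interval at 90%, which applies equally to CRR and ORR. The clause says how to compute the interval, not which proportion to use. Elsewhere the SAP names the endpoint by cohort when it means to: the central-imaging sensitivity analysis in 3.2.3 lists CRR for A and ORR for C1.

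*How different the two endpoints are.* Master protocol 2.2.1 reports, for anti-PD1 monotherapy in relapsed or refractory Hodgkin lymphoma, ORR of 65-87% and CRR of 16-17%. In 25 participants:

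- ORR: 25 × 0.65 = 16.3 to 25 × 0.87 = 21.8 responders
- CRR: 25 × 0.16 = 4.0 to 25 × 0.17 = 4.3 complete responders

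These are background rates, not forecasts for the combination, but they show that one endpoint cannot stand in for the other.

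*Precision.* In a category of 5, the size below which 3.7.2 allows merging, the 90% Clopper-Pearson intervals are:

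- 1 of 5 (20%): 1.0% to 65.7%
- 0 of 5 (0%): upper limit 1 − 0.05^(1/5) = 45.1%

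Subgroup results will be weak for either endpoint.

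**2. Total sample size.** Inputs: 25 in Cohort A (SAP 1.1; Substudy 01, 9.2) and 25 in Cohort C1 (SAP 1.1; Substudy 03, 9.2).

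The other figures in Section 4 reproduce at N = 25:

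- Probability of at least one event, 1 − (1 − p)^25: 22.2% at p = 1%, 39.7% at 2%, 72.3% at 5%, as stated. At N = 75 they would be 52.9%, 78.0% and 97.9%.
- 90% Clopper-Pearson: 4/25 = 16% (5.7-33.0%), 5/25 = 20% (8.2-37.5%), 9/25 = 36% (20.2-54.4%), as in Table 10.

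The total does not reproduce: 25 + 25 = 50; 75 − 50 = 25; 75/50 = 1.5. Other readings were tried:

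- *Dropout inflation, 50/(1 − d), rounded up:* 56 at 10%, 63 at 20%, 72 at 30%. It reaches 75 only at d = 1/3, and no dropout rate is stated.
- *Run-in participants added on top, 6 to 10 per cohort:* 50 + 12 = 62 to 50 + 20 = 70. Section 4 in any case counts those treated at the confirmed dose within the cohort total.
- *Three cohorts:* 3 × 25 = 75. This matches, but the SAP has two cohorts.

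**The case against.** The strongest reply is about weight. There is no hypothesis test, power or alpha. The intervals are descriptive, the protocol's statistical sections plan no subgroup analysis that the SAP could breach, and the SAP defines the primary endpoint by cohort several times. On this view a competent programmer would infer CRR for Cohort A, and a reader would see 25 per cohort in the very sentence that says 75. The two slips are also unrelated to each other.

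Much of that is fair and limits the size of the point. It does not remove the conflict: the one sentence that specifies the output names the wrong endpoint for Cohort A, and an inference is not a specification.

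Three narrower objections also stand in part:

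- The 25 per cohort refers to participants at the confirmed safe dose, and the substudy synopses say approximately 25. If the dose were reduced, participants treated at the rejected dose would be extra. The corrected total should therefore be worded as approximate, but this does not explain 75.
- Merging categories below 5 is permitted, not required, so smaller subgroups could be shown. The intervals at n = 5 are an illustration, not a limit.
- A third cohort as the source of 75 is only a possibility. The SAP's baseline table (5.3) lists primary mediastinal B-cell lymphoma, but the master protocol's introduction also names that disease within its scope, so the listing proves nothing.

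**Conclusion.** Both parts hold. SAP 3.7.2 contradicts itself for Cohort A and is consistent for Cohort C1; the one output sentence governs all six factors. SAP Section 4 overstates the planned total by 25 (75 against 50). The second conclusion rests on the SAP's own description of two cohorts of 25, with run-in participants at the confirmed dose counted inside them.

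The consequences are modest. The primary analysis, the per-cohort precision table and the adverse-event probabilities are unaffected, and the figure of 75 drives no other number in Section 4. The subgroup wording is the more important of the two and should be corrected before Cohort A's responses are analysed. The total is an editorial error.

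**What to change.** In SAP 3.7.2, specify the output as CRR for Cohort A and ORR for Cohort C1, each with a two-sided 90% Clopper-Pearson interval. ORR may stay as an additional row for Cohort A, labelled as secondary. In SAP Section 4, change the total to approximately 50, that is, 25 per cohort at the confirmed safe dose. The sponsor should also check the SAP for remnants of a third cohort.

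Two optional tidy-ups in the same revision:

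- Replace the draft categories for number of previous lines, which still carry a question mark and include 0 and 1, with 2 versus 3 or more. Both substudies require at least two previous lines.
- Add CRR for Cohort A to the response-evaluable analysis in 3.2.4, to match 3.2.3.

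The cost is two wording corrections and a few CRR rows in Cohort A's subgroup table. No new data are needed.
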